7.6.2. Prior and Concomitant Hemophilia Specific Medication

As described for prior and concomitant medication, the number and percentage of subjects using prior and concomitant hemophilia specific medication (ongoing and newly started) will be summarized for Safety Population by ATC level 3 and PT.

The individual dose, number of doses, and total daily dose by PT will be summarized for Safety Population, as well.

In addition, prior and concomitant hemophilia (ongoing and newly started) specific medication will be listed.

This document is confidential.

Statistical Analysis Plan for Interventional Studies
Sponsor: Catalyst Biosciences, Inc.; Protocol No.: DLZ-201

8. Efficacy

8.1. Primary Efficacy Endpoint and Analysis

The primary endpoint is the number and percentage of subjects who achieve a steady-state FIX activity level above 12% with daily dosing.

On Day 1, FIX activity level will be assessed at pre-IV dose and repeated 35 (+/- 5) minutes later prior to the SC dose. Subsequent FIX activity assessment will be performed pre-dose on days 2, 3, 7, 14, 21 and 28, and during washout period on days 29, 30, 31, 32, and 33.

Number and percentage of subjects and list of the subjects with a FIX activity level >12% will be summarized during treatment period for the PK and the Safety Population.

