6.5 CONCOMITANT THERAPY

Enrolled subjects will record all concomitant medications administered from the Screening Visit to Study termination (including the date and time of administration) in their diary.

For this protocol, a prescription medication is defined as a medication that can be prescribed only by a properly authorized/licensed clinician. Medications to be reported in the electronic Case Report Form (eCRF) are concomitant prescription medications, over-the-counter (OTC) medications and supplements.]

There are no concomitant medication restrictions.

If an individual has previously been enrolled on a clinical trial evaluating a treatment (as specified in exclusion criteria #3) in clinical investigation he will be permitted to enroll onto this study, provided it is greater than 30 days since exposure to that study drug, or 3-half-lives, whichever is longer, or absence of clinical effect.

The following medications will be permitted during the study:

- In the event of spontaneous or traumatic bleeding, treatment for a spontaneous or traumatic bleeding episode will be permitted using the subject's current prescribed treatment regimen which could be BeneFIX® or Rixubis®.

Dalcinonacog alfa_DLZ-201 VERSION 2.0, Amendment 1

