Treatment of a spontaneous or traumatic bleeding episode: Subjects will use their current prescribed treatment regimen for any spontaneous or traumatic bleed that occurs while on study drug. If treatment for a spontaneous or traumatic bleeding episode is needed, then subjects will contact the clinical investigative team immediately to report the event, treatment dose administered, and determine follow-up plans for that event including whether to arrange for a blood specimen to be drawn (if feasible) before further administration of either study drug or the current prescribed treatment regimen used. Decision whether to continue daily study drug administration will also be determined by the clinical study team after discussion with the Sponsor.

Dose interruption: SC study drug injections will be interrupted if any of the following occurs: a thrombotic event; clinical evidence of inhibitor formation; or laboratory results suggesting a high titer antibody may be developing; trough activity levels >80% where subsequent dosing will be determined in consultation with the Sponsor.

Surgery: If there is an urgent need for a surgical procedure or an event requiring extended (>48 hours) hospitalization, a FIX activity level will be urgently obtained and measured, and the PI will confer with the Sponsor Medical representative regarding the need for any additional treatment and whether study drug requires interruption.

Measurements:

- **PK, PD, and safety assessments:** FIX activity levels, as well as fibrinogen, D-dimer, prothrombin fragment 1+2 (F1+2), and thrombin-antithrombin complexes (TAT). Prothrombin time and activated partial thromboplastin time (aPTT) will be measured at screening and end of study visit only. Genotype testing will be performed at screening.
- **Immunogenicity assays:** Specimens for immunogenicity testing (antibody to CB2679d, BeneFIX®, and neutralizing activity) will be drawn at screening, pre-dose on days 7, 14, 21, 28 and end of study.

If the FIX activity level decreases unexpectedly by more than 25%, ie, IU/dL, as measured by central laboratory, FIX activity levels will be drawn for analysis within 24 hours and immediately sent to the central laboratory. Specimens for fibrinogen, D-dimer, F1+2, and TAT and immunogenicity testing will also be drawn.

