5.3. Pharmacokinetic (PK) Population

The PK population is defined as any subject who was administered at least one week of daily SC dosing and had FIX activity values at four or more time points. The PK data will be listed for this population and used in all PK analyses. The PK data for subjects with protocol deviations affecting the results may be excluded from summaries and analyses. Any protocol deviations pertaining to the validity of PK analyses (and thus inclusion in the PK population) will be determined before the database lock based on a review of all protocol deviations.

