6.3. Missing Data

Missing data will not be imputed in this study. All analyses will be based on available data.

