9.1. PK Sampling Schedule

PK sampling schedule will be specific to each dose administration. The PK data will be measured as FIX activity levels.

During treatment period: On Day 1, PK assessments will be done at pre-IV dose and repeated 35 (\pm 5) minutes later prior to the SC dose. Subsequent PK assessments will be performed pre-dose on days 2, 3, 7, 14, 21 and 28.

Washout Period: PK assessments will be done on Days 29, 30, 31, 32 and 33. Daily FIX activity levels will be measured, unless FIX activity level is known to be < 5% as measured by local laboratory.

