9.4. PK Parameters Derivation: Attainment of Steady State for FIX Activity

Attainment of steady state will be estimated using aggregate assessment of trough concentration if sufficient data will be available.

To assess whether steady state was achieved for FIX activity after daily dosing of CB2679d, aggregate assessment of trough concentration will be used to evaluate attainment of steady state (Maganti et al 2008). The approach is based on the comparison of log-transformed normalized trough concentration values for each dose to the mean of the results for all the following doses.

This analysis will be done using repeated measures analysis only if the data are sufficient to support; i.e., analysis will be carried out only on subjects who have at least 3 valid FIX activity level results out of 6 pre-dose samples). Alternatively, analysis of variance (ANOVA) comparison will be carried out on log-transformed Cmin (concentration at the end of the dosing interval = FIX activity level pre-dosing) pre-dose on days 2, 3, 7, 14, 21 and 28. The following SAS code may be used to conduct the analysis:

PROC MIXED;

CLASS <time> <subject>;

MODEL log_base_e_ <FIX actual level> = <time> /DDFM = KR;

LSMEANS <time>;

RUN;

The DDFM = KR (Kenward Roger) option performs the degrees-of-freedom calculations detailed by Kenward and Roger (1997).

Contrasts will be tested between a time point and the pooled mean over all remaining time points. For example, the following contrasts will be tested as example:

- Day 3 vs Days 7, 14, 21, and 28
- Day 7 vs Days 14, 21, and 28
- Etc.

The first non-significant comparison will be concluded to be the dosing interval at which steady state concentration are attained. The p-value for difference of Least Square Means (LSM), Geometric Mean Ratio, and the 95% confidence interval (CI) for the contrasts will be provided.

This document is confidential.

Statistical Analysis Plan for Interventional Studies
Sponsor: Catalyst Biosciences, Inc.; Protocol No.: DLZ-201

10. Analysis of Pharmacodynamics

PD analysis will be performed using SAS statistical package version 9.4 or higher. PD analysis will be performed for PD and Safety Population.

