15.2.5.2. Table Conventions

Units will be included where available

If the categories of a parameter are ordered, then all categories between the maximum and minimum category are presented in the table, even if n=0 for all treatment groups in a given category that is between the minimum and maximum level for that parameter. For example, the frequency distribution for symptom severity would appear as:

Severity Rating	N
severe	0
moderate	8
mild	3

Where percentages are presented in these tables, zero percentages will not be presented and so counts of 0 will be presented as 0 and not as 0 (0%).

If the categories are not ordered (e.g., Medical History, Reasons for Discontinuation from the Study, etc.), then only those categories for which there is at least 1 subject represented in 1 or more groups are included.

This document is confidential.

Statistical Analysis Plan for Interventional Studies
Sponsor: Catalyst Biosciences, Inc.; Protocol No.: DLZ-201

An Unknown or Missing category are added to each parameter for which information is not available for 1 or more subjects.

Unless otherwise specified, the estimated mean and median for a set of values are printed out to 1 more significant digit than the original values, and standard deviations are printed out to 2 more significant digits than the original values. The minimum and maximum should report the same significant digits as the original values. For example, for systolic blood pressure:

n	XX
Mean (SD)	XX.X (xx.xx)
95% CI	XX.X - XX.X
Median +/- IQR	xx.xx +/- xx.xx
Min - Max	xx.x - xx.x

Percentage values are printed to one decimal place, in parentheses with no spaces, one space after the count (e.g., 7 (12.8%), 13 (5.4%)). Display values that round down to 0.0 to 0.0. Unless otherwise noted, for all percentages, the number of subjects in the analysis set for the treatment group who have an observation will be the denominator. Percentages after zero counts should not be displayed and percentages equating to 100% are presented as 100%, without decimal places.

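### The >12% FIX count in SAP 8.1 has no visible rule for troughs drawn soon after permitted rescue FIX; if one trough can decide a subject's status, a low trough can be credited to CB2679d

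*SAP*

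**What the plan says.** SAP 4.1 and 8.1 define the primary endpoint as the number of subjects reaching a steady-state FIX activity above 12% on daily dosing. The analysis sentence in 8.1 reads: "Number and percentage of subjects and list of the subjects with a FIX activity level >12% will be summarized during treatment period". It applies to both the PK and the Safety Population. SAP 8.3 repeats the count at 30% and 50%.

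On the readout, SAP 9.1 says: "The PK data will be measured as FIX activity levels". No product-specific assay and no correction for other FIX products is described. Protocol 6.5 (version 2.0) allows a bleed to be treated with the subject's "current prescribed treatment regimen which could be BeneFIX® or Rixubis".

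The nearest provisions are these:

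- SAP 6.3, in a section on not imputing missing values: "All analyses will be based on available data".
- SAP 5.3: "The PK data for subjects with protocol deviations affecting the results may be excluded from summaries and analyses".
- SAP 9.3.2 lets the PK specialist flag and drop unreliable derived PK parameters. Its exclusion of subjects again depends on a protocol deviation.
- SAP 9.4, for the steady-state model: "analysis will be carried out only on subjects who have at least 3 valid FIX activity level results out of 6 pre-dose samples". It does not define which results are valid.
- SAP 7.6.2 summarises and lists hemophilia medication without linking it to FIX samples.
- SAP 3.3, after a treated bleed, leaves the team to decide "whether to arrange for a blood specimen to be drawn (if feasible) before further administration of either study drug"; the sentence goes on to include the prescribed product as well. This concerns sampling, is optional, and leads to no analysis rule.
- SAP 15.2.5.2, for percentages: "the number of subjects in the analysis set for the treatment group who have an observation will be the denominator".

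**The concern.** The endpoint attributes a FIX level to daily CB2679d, but the measured activity includes whatever FIX the subject has infused. A subject may bleed at a low level, treat himself as permitted, and attend a scheduled pre-dose visit a day or two later. Nothing in 8.1 stops that value from counting as a CB2679d result.

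The neighbouring provisions do not reach the count. SAP 5.3 is discretionary and depends on a protocol deviation, and permitted rescue is not one. SAP 9.3.2 concerns derived parameters, and 9.4 governs only the steady-state model. The Safety Population count carries no such exclusion at all.

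The main route is an ordinary scheduled trough that happens to follow an infusion. The route through unscheduled visits is narrow: under SAP 6.4 the scheduled visit must be absent, and the substitute must be a pre-dose sample within the ±1 day window.

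Rescue can only raise FIX, so the error runs one way, in a subject in whom the drug may have failed. The study is meant to guide the starting SC dose for later studies (SAP 3.5).

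**Working it through.** The plan gives no figure to reproduce: SAP 3.5 makes no formal sample size calculation, and neither document states a bleed rate, a rescue dose or a recovery.

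**Inputs from the documents.** rFIX half-life about 18 h (Protocol 2.2); threshold 12% (SAP 8.1); 6 subjects (SAP 3.5).

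**Assumptions.** A rescue infusion raises FIX by R = 20 to 50 points, adds to the true trough T, and decays with an 18 h half-life for either product. Illustrative troughs are T = 2%, 5% and 8%, the same on each day.

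**Step 1: how long a low trough reads above 12%.** Observed level = T + R × 2^(−t/18). It exceeds 12 while t < 18 × log2(R/(12 − T)). For two infusions 24 h apart, R is multiplied by 1 + 2^(−24/18) = 1.397, and time runs from the second infusion.

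| True trough | One infusion, R = 20 to 50 | Two infusions, R = 20 to 50 |
|---|---|---|
| 2% | 18.0 to 41.8 h | 26.7 to 50.5 h |
| 5% | 27.3 to 51.1 h | 35.9 to 59.7 h |
| 8% | 41.8 to 65.6 h | 50.5 to 74.3 h |

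**Step 2: whether one raised trough changes a subject's status.** This depends on a per-subject rule that 8.1 does not give. Take a sample 24 h after one infusion, when a fraction 2^(−24/18) = 0.397 of the rise remains.

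- *Any steady-state trough above 12%.* Needs R > (12 − T)/0.397, which is 25.2 (T = 2), 17.6 (T = 5) or 10.1 (T = 8). A 20-point rise on a 2% trough is therefore not enough: 2 + 7.9 = 9.9%.
- *Mean of Days 14, 21 and 28 above 12%.* Needs R > 3 × (12 − T)/0.397, which is 75.6 (T = 2), 52.9 (T = 5), 30.2 (T = 8) or 15.1 (T = 10). Within 20 to 50 points, status does not change for T of 5% or less. For T = 8 and R = 50, the raised trough reads 27.8 and the mean is (8 + 8 + 27.8)/3 = 14.6. With R = 20 it reads 15.9 and the mean is 10.6.
- *All troughs above 12%.* One raised trough does not change status, because the others stay at T. This uses the constant trough assumed above; a subject whose only low trough was the raised one lies outside the calculation.

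**Step 3: weight of one subject.** 1/6 = 16.7 points. For example, 5/6 = 83.3% becomes 4/6 = 66.7%.

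**Step 4: frequency.** It cannot be derived without a bleed rate and a rescue dose.

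**The case against.** The strongest reply is that this point depends on a larger gap: 8.1 gives no per-subject rule. That is correct, and the point is conditional for that reason. If any treatment-period value counted, the Day 1 sample after the IV load might settle a subject's status before any rescue. That is a separate matter, although defining the counted troughs would resolve both.

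The size also rests on an assumed rise, and low troughs are not shown to be typical. Protocol 2.2.2 reports a median of 15.7% after six daily doses of 150 IU/kg, with four of five subjects above 12%, and a nadir of 20% followed by levels above 30% in both subjects of cohort 6. On the other side, the daily dose here is 100 IU/kg and both cohort 6 subjects developed neutralizing antibodies. Low troughs are possible; the documents do not say how likely.

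The study is small and descriptive. Achievers, FIX levels with actual sampling times, hemophilia medication and bleeds are all listed, so a reader could find a raised trough by cross-reading six subjects. This lowers the stakes. It remains a check made after the results are known, with no agreed window.

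A blanket bar on post-rescue values would over-correct. At 72 h a 50-point rise leaves 50/16 = 3.1 points, so an observed 30% would still be 26.9% without it. That objection stands, and the fix below uses a deduction instead.

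A reader might infer that SAP 6.3 requires contaminated values to be counted. It is mainly a no-imputation rule; the gap comes from the silence of 8.1.

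**Conclusion.** The gap is real and should be closed, but it is conditional. As 8.1 is written, a low steady-state trough drawn roughly 1 to 3 days after rescue can be credited to CB2679d if one trough can decide a subject's status. For steadily low troughs, the effect covers only part of the assumed range under a mean and is absent under an all-troughs rule. Each reclassified subject is worth 16.7 points, always in the drug's favour.

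This rests on the 18 h half-life, an assumed 20 to 50 point rise, and simple addition to the trough.

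A reader might infer that the primary result will be inflated, or that every rescued subject becomes an achiever. The documents support neither: frequency is unknown, and several combinations in the working leave status unchanged. Nor is the plan without protection, since 9.3.2 and the validity condition in 9.4 give partial, discretionary cover for the PK parameters and the steady-state model.

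The statement concerns the visible text. Some pages around the Note to File were not available, and the table shells are a separate document.

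**What to change.** 1. In 8.1 and 8.3, state that the >12%, >30% and >50% counts use steady-state pre-dose troughs, name the days, and say how a subject's troughs are combined.
2. From diary product, amount, date and time, flag any FIX value drawn within a pre-specified window after non-study FIX, for example five half-lives of that product (90 h at 18 h, when R/32 = 0.6 to 1.6 points remain).
3. Do not count a flagged value above the threshold as achievement unless it stays above after a pre-specified conservative deduction for residual rescue FIX. Keep a flagged value at or below the threshold as it is, since rescue can only raise the level. Judge the subject on his remaining unflagged troughs.
4. Exclude flagged values from the 9.4 model, defining valid accordingly, and from washout half-life, CL and Vz. In 6.4, do not let a flagged unscheduled sample replace a scheduled trough.
5. Report a sensitivity count using all values. Show any subject with no evaluable trough explicitly, with results both with and without him in the denominator, as a stated exception to 15.2.5.2. The choice matters: 4/5 against 4/6 is 80.0% against 66.7%, a difference of 13.3 points.

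**Cost.** SAP wording in several sections, one derived flag and one deduction rule, whose recovery and half-life must be fixed in advance. The diary already records the infusion details (Protocol 8.2.1) and is entered into the eCRF (Protocol 10.1.7).

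**Downside.** Some troughs lose evaluability. With a 90 h window, one infusion at a random time in the week before a given weekly trough flags it with probability 90/168 = 54%; two infusions 24 h apart give 114/168 = 68%. A single infusion can touch at most one of the four weekly troughs, because their minimum spacing with the ±1 day windows is Day 8 to Day 13, or 120 h. Repeat infusions can touch two if they span at least 120 − 90 = 30 h at that spacing, or 168 − 90 = 78 h at nominal spacing. Bleed treatment is unchanged.

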4.1. Primary Efficacy Endpoint

The primary endpoint is:

- Number of subjects who achieve a steady-state FIX activity level above 12% with daily dosing.

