5.2. Safety Population

The Safety Population will include all subjects who were administered at least one dose of study medication. Subjects will be analyzed according to treatment received. The Safety Population will be used for all analyses of efficacy in respect to PK and PD and safety endpoints and for the presentation of subjects in subject listings.

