6.4. Visit Windows

All data will be organized and analyzed according to the scheduled visits outlined in the protocol. However, if the scheduled visit is not available in the dataset, unscheduled visit will be mapped to a scheduled visit for analysis using the date and/or time of collection/assessment to mapped to the intended visit using the visit window specified below.

If more than one record occurs within the same visit window where only one assessment is expected, then the following rule should be applied: for pre-study assessments the last non-missing result prior to study drug administration should be used; for post-treatment assessments the closest non-missing result to the scheduled visit should be used.

Visit in Protocol	Time point	Time Window	Visit Window
Day 1	Pre IV dose	no limitation	no window as only one day
	Post IV dose, pre SC Dose	35 +/- 5 minutes post IV dose, - 5 minutes pre SC dose	no window as only one day
Day 2 – Day 3	Pre SC dose	- 5 minutes pre SC Dose	no window as only one day

This document is confidential.

Statistical Analysis Plan for Interventional Studies
Sponsor: Catalyst Biosciences, Inc.; Protocol No.: DLZ-201

Day 4 – Day 28	Pre SC dose	- 5 minutes pre SC Dose	+/- 1 days
----------------	-------------	-------------------------	------------

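### SAP 8.1 names a steady-state FIX >12% primary endpoint, but its counting rule accepts any treatment-period level >12% and does not say which samples qualify

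*SAP*

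**What the plan says.** SAP 4.1 gives the endpoint as "Number of subjects who achieve a steady-state FIX activity level above 12% with daily dosing", and SAP 8.1 opens in the same terms: "The primary endpoint is the number and percentage of subjects who achieve a steady-state FIX activity level above 12% with daily dosing". Protocol 9.4.2 matches. Neither document defines steady state for a subject.

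The analysis sentence in 8.1 is different. It summarises and lists subjects "with a FIX activity level >12% will be summarized during treatment period", in both the PK and the Safety Population. It names no visit, no restriction to troughs and no number of qualifying samples. The titles of Tables 14.2.1.1 and 14.2.1.2 follow the analysis sentence and omit steady state.

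SAP 9.1 settles which samples fall in the treatment period. Its list begins "During treatment period: On Day 1, PK assessments will be done at pre-IV dose and repeated 35" minutes later, ahead of the SC dose, and continues with pre-dose samples on Days 2, 3, 7, 14, 21 and 28. Days 29 to 33 are placed in washout.

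On populations, SAP 5.2 states "The Safety Population will include all subjects who were administered at least one dose of study medication", and SAP 5.3 admits "any subject who was administered at least one week of daily SC dosing and had FIX activity values at four or more time points".

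SAP 9.4 assesses attainment of steady state from the pre-dose samples by aggregate contrasts, provided there are enough data. Its output is one dosing interval for the group, reported in Tables 14.2.3.x.

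**The concern.** The endpoint and the rule that counts it are not the same quantity. The endpoint is about a plateau on daily SC dosing. The rule asks whether a level above 12% occurred within the treatment period, and that period contains a sample that reflects the IV load alone and early troughs taken before SC accumulation is complete.

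The populations do not close the gap, because they select subjects and not samples. In the Safety Population, a subject who received only the IV load could be counted. In the PK Population, a subject with no sample after Day 7 could be counted.

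SAP 9.2 shows that the IV phase was recognised as a separate matter: it takes the peak activity only after the low point that follows the infusion. That separation is not carried into 8.1. SAP 13 declares no change to the endpoint, and the available Note to File entries pass from 6.2.1 to 8.2.1 without touching 8.1.

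At stake is the single primary result of a six-subject study which, by SAP 3.5, is meant to guide the starting SC dose of later studies.

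**Working it through.** There is no stated calculation to reproduce; the sample size of 6 is justified descriptively. The check is which samples the rule admits and what each one represents.

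**1. The post-IV sample.** The load is 50 IU/kg (SAP 3.7). The level exceeds 12% when recovery × 50 > 12, that is, when recovery > 12/50 = 0.24 IU/dL per IU/kg. With a baseline of 2% the threshold is (12 − 2)/50 = 0.20. The documents give no IV recovery. An assumed 0.5 to 1.0 would give 25% to 50%. The same sample would pass the 30% and 50% cut-offs of SAP 8.3 at recoveries above 30/50 = 0.60 and 50/50 = 1.00.

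**2. The troughs.** Protocol 2.2.2 gives a half-life of 63.2 h after repeated SC dosing and 66-103 h after single SC doses. For a one-compartment model with uninterrupted daily dosing and the load ignored, the fraction of SC steady state at a trough after n doses is 1 − 2^(−24n/t½).

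| Pre-dose sample | n | t½ 63.2 h | t½ 103 h |
|---|---|---|---|
| Day 2 | 1 | 0.231 | 0.149 |
| Day 3 | 2 | 0.409 | 0.276 |
| Day 7 | 6 | 0.794 | 0.621 |
| Day 14 | 13 | 0.967 | 0.877 |
| Day 20 (Day 21 less 1 day) | 19 | 0.993 | 0.954 |
| Day 21 | 20 | 0.995 | 0.960 |
| Day 28 | 27 | 0.999 | 0.987 |

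Days 2, 3 and 7 are not SC steady-state samples. The earliest of them also carry some of the IV load, by an amount the text does not allow one to fix because it gives no IV half-life for CB2679d. Days 21 and 28 are at 95% or more in every case, even with the one-day-early window.

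**3. Could the choice of samples change the count?** Protocol 2.2.2 offers two sources, and they point in different directions.

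- Cohort 5, no load, 150 IU/kg daily: median 15.7% after six doses, with four of five subjects above 12%. Scaled linearly to 100 IU/kg, the steady-state median is 15.7/0.794 × 100/150 = 13.2%. It is 12.9% at t½ 60.2 h and 15.7/0.621 × 100/150 = 16.9% at 103 h. If 15.7% was the 6-hour sample and not the 24-hour one, multiplying by 2^(−18/63.2) gives 10.8% (10.5% at 60.2 h). That step assumes instant absorption and so is a lower bound.
- Cohort 6, load plus SC, two subjects: levels rose above 30%. Linear scaling keeps this above 12% at 100 IU/kg for any cohort 6 SC dose up to 30 × 100/12 = 250 IU/kg. The cohort 6 dose is in a figure that is not shown, and both subjects developed neutralizing antibodies.

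The first source puts the median near the cut-off, so the two counts could differ. The second suggests that they could agree.

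**4. Interrupted dosing.** One missed dose leaves the next trough at 2^(−24/63.2) = 0.769 or 2^(−24/103) = 0.851 of its previous value. A subject would need 12/0.769 = 15.6% or 12/0.851 = 14.1% beforehand to stay above 12%.

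**The case against.** The strongest reply is that 8.1 should be read whole. Its opening sentence refers to steady state and daily dosing, and a sample drawn before the first SC dose is neither. SAP 9.4 supplies a steady-state method that uses pre-dose samples only. SAP 6.4 says "All data will be organized and analyzed according to the scheduled visits outlined in the protocol", so the table may show counts by visit. The study is descriptive, no decision rule depends on the count, and levels are summarised by time point and listed by subject, so a reader can rebuild any version of it.

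Much of this stands. The intent is clear, and the SAP does not direct the analyst to count the post-IV sample; it fails to exclude it. Steady state is not absent from the SAP; what is missing is a link to 8.1 and a per-subject rule. A bare cross-reference to 9.4 would not supply that rule, since 9.4 returns a group interval, and only if data are sufficient. A by-visit table would give several counts with none named as primary, in an open-label study. The IV-only subject is an edge case confined to the Safety Population.

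A reader might infer that the primary result will be inflated, or that all six subjects will be counted on the load. The documents do not support that. IV recovery is not given, the table shells are in a separate document that was not available, and the two earlier cohorts point in different directions.

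**Conclusion.** The point holds as a mismatch between the named endpoint and the rule that counts it. Followed as written, the rule can credit a subject on the IV load alone, or on a trough at 15% to 79% of SC steady state, so it need not measure the endpoint it reports.

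That conclusion rests on the text. The 0.24 threshold is plain arithmetic, but whether subjects exceed it depends on a recovery that must be assumed. The steady-state fractions assume one compartment, no missed doses and no contribution from the load. The effect on the reported count is uncertain, and no count is forecast. Because the data are listed, the harm is to the definition of the primary result and not to the data. It still needs correcting, since this is the only primary endpoint.

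**What to change.** In SAP 8.1 and Tables 14.2.1.x:

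- Base the primary count on the pre-dose troughs at Day 21 and Day 28, and exclude the Day 1 to Day 7 samples. Day 14, at 88-97% of steady state, is not needed. Day 29 is left out because the SAP places it in washout and the window table in 6.4 stops at Day 28.
- Count a subject as achieving the endpoint only if every available late trough is above 12%. A mean would be too lenient: 22% followed by 8% has a geometric mean of √(22 × 8) = 13.3% and would pass.
- Name one population and one count as primary. Use subjects with at least one late trough as the denominator, in keeping with SAP 6.3 ("All analyses will be based on available data") and the percentage convention in 15.2.5.2, and report how many subjects have none.
- Flag late troughs that follow missed doses, or non-study FIX within a window fixed before database lock, and give a sensitivity count without them. Counting subjects with no late trough as not achieving the endpoint is an optional further sensitivity count.
- Keep the any-time >12% count and the 8.3 counts as labelled descriptive tables.

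All samples are already scheduled, so the cost is SAP wording and table programming. The downside is that the reported rate may be lower than the any-time count, and one low late trough is enough for a subject not to count.
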